## **6.5 Criteria for Removal from Study**

Patients will be removed from study when any of the criteria listed in Section 6.3 applies. The reason for study removal and the date the patient was removed must be documented in the Case Report Form that will be submitted to our institution IRB.

# **7. DOSING DELAYS/DOSE MODIFICATIONS**

## **Dosage adjustment guidelines for toxicities**

All dose adjustments should be based on the worst preceding toxicity, graded using the National Cancer Institute Common Toxicity Criteria (version 4.0).

Once a dose is decreased, re-escalation is not permitted. Patients will be taken off study if they develop the same grade 4 toxicity despite a first dose reduction. The dose of leucovorin is not modified for toxicity.

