### **7.1 Hematologic toxicity**

Do not retreat until the granulocyte count is  $\geq 1.5 \times 10^9/L$  and the platelet count is  $\geq 75 \times 10^9/L$ .

Blood counts at Day 1	Delay of cycle	Dose reduction		
		Irinotecan	Oxaliplatin	Fluorouracil
Granulocytes <math>< 1.5 \times 10^9/L</math>	Hold treatment until granulocytes $\geq 1.5 \times 10^9/L$ (one or two weeks if necessary). In case of non-recovery after 2 weeks delay, stop treatment*	1 st occurrence: reduction of dose to $150 \text{ mg/m}^2$ 2 nd occurrence: maintain the dose at $150 \text{ mg/m}^2$ 3 rd occurrence: treatment discontinuation	1 st occurrence: no reduction of dose 2 nd occurrence: reduce the dose to $60 \text{ mg/m}^2$ 3 rd occurrence: treatment discontinuation	N/A
Platelets <math>< 75 \times 10^9/L</math>	Hold the treatment until recovery (platelets $\geq 75 \times 10^9/L$ ). In case of non-recovery after 2 weeks delay, stop treatment	1 st occurrence : no reduction of dose 2 nd occurrence: reduce the dose to $150 \text{ mg/m}^2$ 3 rd occurrence: treatment discontinuation	1 st occurrence: reduce the dose to $60 \text{ mg/m}^2$ 2 nd occurrence: maintenance of the reduced dose 3 rd occurrence: treatment discontinuation	1 st occurrence: the continuous infusion to 75% of the original doses

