**7.1b. According to the low nadir blood counts or in case of infection**

ADVERSE EVENTS	REDUCTION OF DOSE FOR SUBSEQUENT CYCLES
Febrile neutropenia	1 st occurrence: reduce the dose of irinotecan to $150 \text{ mg/m}^2$
Grade 4 neutropenia during more than 7 days	2 nd occurrence: reduce also the dose of oxaliplatin to $60 \text{ mg/m}^2$ 3 rd occurrence: treatment discontinuation
Infection with concomitant grade 3-4 neutropenia	
Grade 3-4 thrombocytopenia	1 st occurrence: reduce the oxaliplatin dose to $60 \text{ mg/m}^2$ and the continuous 5-FU dose to 75 % of the original dose 2 nd occurrence: reduce also the dose of irinotecan to $150 \text{ mg/m}^2$ and the dose of continuous 5FU of additional 25 % 3 rd occurrence: treatment discontinuation

Use Filgrastim or pegfilgrastim for recurrent grade 3/4 neutropenia despite a first-dose reduction or after febrile neutropenia.

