## 7.2. Gastrointestinal toxicities

Patients must be instructed in the use of loperamide as treatment for diarrhea, and must have a supply of this drug upon starting FOLFIRINOX. Patients should not be retreated with irinotecan until recovery from diarrhea (without loperamide for at least 24 h) has occurred.

ADVERSE EVENTS	REDUCTION OF DOSE FOR SUBSEQUENT CYCLES
Diarrhea grade 3-4 or Diarrhea + fever and/or neutropenia grade 3-4	1 st occurrence: reduce the irinotecan dose to 150 mg/m   2 nd occurrence: reduce also the oxaliplatin dose to 60 mg/m  and reduce the dose of continuous 5FU to 75 % of the original dose  3 rd occurrence: investigator's discretion
Diarrhea ≥ 48 h despite high doses loperamide	No systematic reduction of the irinotecan, oxaliplatin or 5FU doses after complete recovery, unless grade 3-4 diarrhea, or diarrhea + fever, and/or concomitant neutropenia grade 3-4

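### Section 7 removes a patient whose grade 4 toxicity recurs after a first dose reduction, while Tables 7.1b and 7.2 re-dose the same patient, and no text says which rule prevails

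*Combined protocol and SAP*

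**What the plan says.** The general rule stands at the head of Section 7, before any table and without exception: "Patients will be taken off study if they develop the same grade 4 toxicity despite a first dose reduction".

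Table 7.1b has a row for "Grade 4 neutropenia during more than 7 days". The first occurrence lowers irinotecan to 150 mg/m2. The second continues treatment with a further cut ("occurrence: reduce also the dose of oxaliplatin to" 60 mg/m2). Discontinuation comes at the third. The row for grade 3-4 thrombocytopenia follows the same pattern: oxaliplatin and 5-FU are lowered first, the second step is "occurrence: reduce also the dose of irinotecan to" 150 mg/m2 with a further 5-FU cut, and treatment stops at the third.

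Table 7.2, for grade 3-4 diarrhea, lowers irinotecan first. At the second occurrence the instruction is to "reduce also the oxaliplatin dose to 60 mg/m"2 and to cut 5-FU. The third is left to the investigator.

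Below Table 7.1b is the growth-factor instruction: "Use Filgrastim or pegfilgrastim for recurrent grade 3/4 neutropenia despite a first-dose reduction or after febrile neutropenia".

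**The concern.** A repeat of the same grade 4 event after a dose reduction is the situation in which a dosing section most needs to give one answer. Here it gives two. The error can run in only one direction that matters for safety. Stopping is always open to the physician, so following Section 7 breaches nothing; following the tables means more chemotherapy for a patient whom Section 7 has already removed. The protocol's own irinotecan warnings (Section 9.1.4) mention septic deaths after severe myelosuppression and describe severe diarrhea as capable of being fatal.

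There is also a conduct problem. Section 14.4 calls for monitoring of compliance with the protocol, and Section 14.5 asks that deviations be avoided. A monitor looking at such a patient could not say which action complied. For the analysis, time to treatment failure (Section 11.3) ends when the patient leaves the study for whatever cause, so its value for such a patient depends on which rule the physician followed.

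**Working it through.** This is mainly a comparison of texts; the arithmetic is limited to the doses given under the tables.

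**Step 1: follow one patient.** The patient has grade 4 neutropenia for more than 7 days. Table 7.1b lowers irinotecan to 150 mg/m2, which is a first dose reduction. The same event then recurs. Under Section 7 the patient leaves the study. Under Table 7.1b the patient continues with oxaliplatin lowered as well. This row contains no grade 3 case, so the two rules cannot be reconciled by assigning the table step to grade 3 events.

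**Step 2: check that table layout does not create the clash.** In the available text the three neutropenia rows appear to share one set of steps. Whether they share it or the later steps belong to the grade 4 row alone, the second occurrence leads to a reduction and not to removal. If occurrences are pooled across the three events, the clash is confined to sequences in which both events are the same grade 4 toxicity. It does not arise when, for example, febrile neutropenia came first.

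**Step 3: look for the same pattern elsewhere.** The thrombocytopenia row of 7.1b and the diarrhea row of 7.2 cover grades 3 and 4 together, so each clashes with Section 7 when both events are grade 4. The growth-factor sentence assumes continued treatment after recurrent neutropenia and clashes only when both episodes are grade 4. The Day-1 count table in 7.1 also continues treatment at the second occurrence (irinotecan for granulocytes: "occurrence: maintain the dose at" 150 mg/m2; oxaliplatin for platelets: "occurrence: maintenance of the reduced dose"). Its thresholds have no lower limit, but it names no toxicity grade, so it is not counted here as a further conflict.

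**Step 4: look for a ranking.** Section 7 says that adjustments follow the worst earlier toxicity. That identifies the toxicity that drives an adjustment, not the rule that wins. Section 6.3 lists stopping criteria, including unacceptable adverse events; Section 6.5 refers back to that list; Discontinuation of Therapy requires withdrawal when continuing is not in the patient's interest. None of these, and nothing in Section 12, ranks Section 7 against the tables.

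**Step 5: doses at the second occurrence under the tables.** Planned doses (Section 6.1) are irinotecan 165, oxaliplatin 85 and 5-FU 2400 mg/m2.

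- Irinotecan 150 in all three rows: (165 - 150)/165 = 9.1% lower.
- Oxaliplatin 60 in all three rows: (85 - 60)/85 = 29.4% lower.
- 5-FU, neutropenia row: unchanged at 2400.
- 5-FU, diarrhea row: 0.75 x 2400 = 1800.
- 5-FU, thrombocytopenia row: 0.50 x 2400 = 1200 if the second 25% cut is taken from the original dose, or 0.75 x 0.75 x 2400 = 1350 if taken from the reduced dose.

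Under Section 7 the patient receives no further dose.

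**Step 6: trace the effect on the endpoints.** The Simon design in Section 12.2 (12 then 16 patients, stopping at 3 or fewer responses in stage 1, failure at 11 or fewer overall) uses none of these rules. Scans continue every 8 weeks for patients off treatment (Section 6.4; Section 10, note d). Time to treatment failure is the endpoint tied to discontinuation. It is secondary, and Section 12.4 only summarizes time-to-event variables, by Kaplan-Meier.

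**The case against.** The strongest reply is that a coherent reading exists. The Section 7 sentence is mandatory and narrow, so it can be taken as an overriding stop; the second and third table steps then still serve grade 3 repeats and mixed sequences, and neither rule is empty. That reading is sensible, but the protocol does not state it. The opposite reading, that a specific table overrides a general sentence, is equally available. For prolonged grade 4 neutropenia the table step addresses exactly the case that Section 7 removes, so a physician reading the table has reason to think it governs.

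It can also be said that the tables lower doses, that 7.1 requires count recovery before retreatment, that growth factor is directed, and that the safety committees in Section 14.3 review events. This is correct and lowers the risk per patient. It does not tell the physician what to do.

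Three stronger inferences should be resisted. First, because the third diarrhea step is discretionary, a reader might infer that Section 7 is the only mandatory stop there. It is not: Section 6.5, through the criteria in 6.3, and Discontinuation of Therapy are worded as obligations, although they depend on judgement. Second, a reader might apply the rates in Section 8.1 to 28 patients to count those affected. Those rates combine grades 3 and 4, come from pancreatic adenocarcinoma, and do not count repeated grade 4 events, so they give neither an estimate nor a safe upper limit. Third, a reader might extend the conflict to the Day-1 rows on equal terms. Those rows name no grade, and one entry carries an asterisk whose note does not appear in the available text.

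**Conclusion.** The conflict is real and should be corrected. It is certain on the text for repeated grade 4 neutropenia lasting more than 7 days, and it extends to repeated grade 4 events within the thrombocytopenia row of 7.1b and the diarrhea row of 7.2. For an affected patient the difference is between no further chemotherapy and a cycle with irinotecan about 9% and oxaliplatin about 29% below plan, plus 5-FU at between half and the full planned dose.

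How many patients this touches is unknown and may be none. A reader might infer that the trial's primary conclusion is at risk; the documents do not support that, because the design figures and stopping boundaries do not rest on these rules. The point concerns patient safety and clear conduct, with a possible small effect on one descriptive secondary endpoint. The conclusion assumes only that the neutropenia rows of 7.1b are read in one of the two ways set out above, and both give the same answer.

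**What to change.** Default: add after the Section 7 sentence: *This rule takes precedence over the occurrence steps in 7.1, 7.1b and 7.2 when both events are the same grade 4 toxicity; those steps apply to grade 3 recurrences and to mixed sequences.* Naming 7.1 covers any grade 4 count found on Day 1. In the growth-factor sentence under 7.1b, after the reference to a first dose reduction, insert: *(unless Section 7 takes the patient off study for recurrent grade 4 neutropenia)*. The febrile-neutropenia clause stays as it is, in agreement with Section 6.2.

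Alternative, if the investigator intends the tables to govern hematologic toxicity: insert *non-hematologic* before *toxicity* in the Section 7 sentence and add that hematologic toxicity is managed by the steps in 7.1 and 7.1b. Section 7 should then also say that it prevails over 7.2 for repeated grade 4 diarrhea; otherwise the clash remains there. The growth-factor sentence needs no change under this option.

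Either is a wording amendment with no new visit, procedure or change in sample size. The default has a clinical cost: patients with recurrent grade 4 toxicity, including grade 4 neutropenia of any duration, stop earlier than under the tables and lose some treatment exposure. The investigator should weigh that cost in choosing between the two.

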### **7.1 Hematologic toxicity**

Do not retreat until the granulocyte count is  $\geq 1.5 \times 10^9/L$  and the platelet count is  $\geq 75 \times 10^9/L$ .

Blood counts at Day 1	Delay of cycle	Dose reduction		
		Irinotecan	Oxaliplatin	Fluorouracil
Granulocytes <math>< 1.5 \times 10^9/L</math>	Hold treatment until granulocytes $\geq 1.5 \times 10^9/L$ (one or two weeks if necessary). In case of non-recovery after 2 weeks delay, stop treatment*	1 st occurrence: reduction of dose to $150 \text{ mg/m}^2$ 2 nd occurrence: maintain the dose at $150 \text{ mg/m}^2$ 3 rd occurrence: treatment discontinuation	1 st occurrence: no reduction of dose 2 nd occurrence: reduce the dose to $60 \text{ mg/m}^2$ 3 rd occurrence: treatment discontinuation	N/A
Platelets <math>< 75 \times 10^9/L</math>	Hold the treatment until recovery (platelets $\geq 75 \times 10^9/L$ ). In case of non-recovery after 2 weeks delay, stop treatment	1 st occurrence : no reduction of dose 2 nd occurrence: reduce the dose to $150 \text{ mg/m}^2$ 3 rd occurrence: treatment discontinuation	1 st occurrence: reduce the dose to $60 \text{ mg/m}^2$ 2 nd occurrence: maintenance of the reduced dose 3 rd occurrence: treatment discontinuation	1 st occurrence: the continuous infusion to 75% of the original doses

**7.1b. According to the low nadir blood counts or in case of infection**

ADVERSE EVENTS	REDUCTION OF DOSE FOR SUBSEQUENT CYCLES
Febrile neutropenia	1 st occurrence: reduce the dose of irinotecan to $150 \text{ mg/m}^2$
Grade 4 neutropenia during more than 7 days	2 nd occurrence: reduce also the dose of oxaliplatin to $60 \text{ mg/m}^2$ 3 rd occurrence: treatment discontinuation
Infection with concomitant grade 3-4 neutropenia	
Grade 3-4 thrombocytopenia	1 st occurrence: reduce the oxaliplatin dose to $60 \text{ mg/m}^2$ and the continuous 5-FU dose to 75 % of the original dose 2 nd occurrence: reduce also the dose of irinotecan to $150 \text{ mg/m}^2$ and the dose of continuous 5FU of additional 25 % 3 rd occurrence: treatment discontinuation

Use Filgrastim or pegfilgrastim for recurrent grade 3/4 neutropenia despite a first-dose reduction or after febrile neutropenia.

## 7.2. Gastrointestinal toxicities

Patients must be instructed in the use of loperamide as treatment for diarrhea, and must have a supply of this drug upon starting FOLFIRINOX. Patients should not be retreated with irinotecan until recovery from diarrhea (without loperamide for at least 24 h) has occurred.

ADVERSE EVENTS	REDUCTION OF DOSE FOR SUBSEQUENT CYCLES
Diarrhea grade 3-4 or Diarrhea + fever and/or neutropenia grade 3-4	1 st occurrence: reduce the irinotecan dose to 150 mg/m   2 nd occurrence: reduce also the oxaliplatin dose to 60 mg/m  and reduce the dose of continuous 5FU to 75 % of the original dose  3 rd occurrence: investigator's discretion
Diarrhea ≥ 48 h despite high doses loperamide	No systematic reduction of the irinotecan, oxaliplatin or 5FU doses after complete recovery, unless grade 3-4 diarrhea, or diarrhea + fever, and/or concomitant neutropenia grade 3-4

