## **6. TREATMENT PLAN**

### **6.1 FOLFIRINOX Administration**

Treatment will be administered on an outpatient basis. Reported adverse events and potential risks are described in Section 8. Appropriate dose modifications for each of the components of *FOLFIRINOX* are described in Section 7. No investigational or commercial agents or therapies other than those described below may be administered with the intent to treat the patient’s malignancy.

The *FOLFIRINOX* regimen consists of oxaliplatin at a dose of 85 mg per square meter, given as a 2-hour intravenous infusion, immediately followed by leucovorin at a dose of 400 mg per square meter, given as a 2-hour intra-venous infusion, with the addition, after 30 minutes, of irinotecan at a dose of 165 mg per square meter, given

as a 90-minute intravenous infusion through a Y-connector. This treatment is immediately followed by a continuous intravenous infusion of 2400 mg per square meter of 5-FU over a 46-hour period every 2 weeks. No 5FU intravenous bolus will be given in the attempt to minimize toxicity without compromise efficacy. [28] [29]. Leucovorin will be kept as part of the regimen despite the lack of 5FU bolus.

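### Diarrhea with fever and grade 3-4 neutropenia meets both table 7.1b and table 7.2, which differ on the 5-FU step and on whether a third episode requires stopping, and no rule says which governs

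*Combined protocol and SAP*

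**What the plan says.** Section 6.1 sets the starting 5-FU dose as a "continuous intravenous infusion of 2400 mg per square meter of 5-FU over a 46-hour period every 2 weeks". Section 7 then gives dose changes by type of toxicity, counted by occurrence.

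- **Table 7.1b (nadir counts or infection).** One trigger is "Febrile neutropenia", with no exclusion when diarrhea is present. A neighbouring trigger is "Infection with concomitant grade 3-4 neutropenia". The first occurrence reduces irinotecan. The second reads "occurrence: reduce also the dose of oxaliplatin to" 60 mg/m2 and does not mention 5-FU. The third is discontinuation of treatment.
- **Table 7.2 (gastrointestinal).** One trigger is "Diarrhea + fever and/or neutropenia grade 3-4". The first occurrence reduces irinotecan. The second also reduces oxaliplatin and takes continuous 5-FU to 75% of the original dose. The third reads "occurrence: investigator's discretion".
- **Opening paragraph of Section 7.** Adjustments follow the most severe toxicity seen so far. A patient who has the same grade 4 toxicity again after a first dose reduction leaves the study.

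Neither table refers to the other. Section 7 contains no rule of precedence and no rule for combining tables.

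**The concern.** Table 7.2 makes the combination of diarrhea with fever or severe neutropenia a trigger in its own right, so the overlap with 7.1b is built into the tables. For one serious episode, a treating physician can read a mandatory stop in one table and a discretionary decision in the other.

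Two patients with the same history could therefore be handled differently, depending on which table was opened. A monitor would have no fixed standard for deciding whether continued treatment was a deviation. Time to treatment failure is a secondary endpoint, and Section 11.3 ends it at study discontinuation for any reason, so it would depend in part on the same choice.

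**Working it through.** There is no design figure to reproduce. The check compares the text of the two tables and needs a few multiplications.

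**1. Do the triggers overlap?** Take one episode with diarrhea, fever and grade 3-4 neutropenia. It meets the 7.2 row however its and/or is read. It meets the febrile neutropenia row of 7.1b, on the assumption that fever with grade 3-4 neutropenia is what that row means. If infection is found, it also meets the infection row.

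**2. What does each table require?**

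| Occurrence | Table 7.1b, neutropenia and infection rows | Table 7.2 |
|---|---|---|
| 1st | irinotecan 150 mg/m2 | irinotecan 150 mg/m2 |
| 2nd | also oxaliplatin 60 mg/m2; 5-FU not mentioned | also oxaliplatin 60 mg/m2; 5-FU to 75% of original |
| 3rd | discontinuation | investigator decides |

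This treats the occurrence text in 7.1b as shared by its three neutropenia and infection rows, which is the natural reading because the infection row has no text of its own.

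**3. Size of the 5-FU difference at the second occurrence.** Starting dose 2400 mg/m2 (Section 6.1).
- 7.2: 0.75 × 2400 = 1800 mg/m2.
- 7.1b alone: no change listed, so 2400 mg/m2.
- Difference: 2400 − 1800 = 600 mg/m2 per cycle, and 600/2400 = 25%.

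**4. Do the general rules settle it?** Ranking by worst toxicity does not: the 7.2 trigger contains the 7.1b toxicity, so there are not two separate events to rank. The grade 4 rule acts earlier and differently. The first dose reduction comes at the first occurrence, so a second episode of the same grade 4 toxicity takes the patient off study, at the point where both tables instead prescribe a further reduction. For those patients Section 7 holds three instructions. Repeat episodes that are not the same grade 4 toxicity still reach the third-occurrence difference.

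**5. How many patients?** Section 8.1 gives grade 3-4 rates from pancreatic adenocarcinoma: febrile neutropenia 5%, diarrhea 13%.
- Febrile neutropenia: 28 × 0.05 = 1.4 patients.
- Grade 3-4 diarrhea: 28 × 0.13 = 3.64 patients.

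Under the assumption in step 1, a combined episode is a febrile neutropenia episode, so 1.4 is the ceiling on expected patients with even one. The documents do not give the share who also have diarrhea. Letting it run from 0 to 1 gives 0 to 1.4 patients. The 5-FU difference needs two such episodes in one patient and the stopping difference needs three, if both tables count episodes alike.

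**6. A separate wording gap in 7.1b.** The thrombocytopenia row takes 5-FU to 75% at the first occurrence and cuts a further 25% at the second, without saying of what.
- Of the original dose: 2400 × (0.75 − 0.25) = 1200 mg/m2.
- Of the current dose: 2400 × 0.75 × 0.75 = 1350 mg/m2.

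**The case against.** The best defence is that the tables can be applied together. Table 7.1b gives no 5-FU dose for febrile neutropenia; the 2400 mg/m2 figure is read from its silence. Elsewhere Section 7 says so when a dose is to be held. A site that follows both rows would give 5-FU at 75%, and a site that stops at the third episode satisfies both tables. The grade 4 rule removes some patients earlier, and Section 6.2 makes G-CSF mandatory after febrile neutropenia, which is aimed at repeat episodes.

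Much of this stands, and it rules out several stronger readings that a reader might infer:

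- *The third-occurrence rules are opposites.* They are not. Discretion includes stopping, so the difference is mandatory against optional.
- *Whatever the site does breaches one table.* It does not. Stopping at the third episode complies with both; only continuing conflicts with 7.1b.
- *The protocol states two 5-FU doses for the same event.* It states one, in 7.2. The other is an inference, although a reasonable one: 7.1b names 5-FU where it wants a cut, and table 7.1 marks 5-FU as not applicable for low granulocytes.
- *Tables 7.1 and 7.1b also conflict on platelets.* The documents do not establish this. Table 7.1 is keyed to Day 1 counts and 7.1b to nadir counts. The 5-FU cell in 7.1 ("occurrence: the continuous infusion to 75% of the original doses") shows only a first-occurrence step beside cells that list three, and it may be incomplete in the available text.

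What the defence does not supply is any sentence telling the site to combine the tables, or saying that a mandatory stop in one overrides discretion in the other.

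**Conclusion.** The point holds as an internal inconsistency. One serious episode falls under two tables that differ on stopping at the third occurrence and, if 7.1b is applied alone, on 5-FU at the second (2400 against 1800 mg/m2). The Section 7 rule on recurrent grade 4 toxicity adds a third instruction that neither table acknowledges.

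The reach is small. At most about 1.4 of 28 patients would be expected to have one combined episode, and fewer would have the two or three needed, on the assumption that the pancreatic adenocarcinoma rates carry over. The response-rate test and the two-stage rule are not affected. Any effect on time to treatment failure is limited to those few patients and cannot be put in figures from the documents. The case for acting is individual safety and consistent conduct. The unclear base of the further 25% cut in 7.1b is a minor clarification (1200 against 1350 mg/m2).

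**What to change.** Reconcile the opening paragraph of Section 7 with tables 7.1b and 7.2, so that diarrhea with fever and grade 3-4 neutropenia has a single instruction. The text should state:

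- which table governs, or that both apply and how they combine;
- the resulting 5-FU step at the second occurrence;
- the action at the third occurrence;
- how the off-study rule for recurrent grade 4 toxicity fits with both tables.

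As a minor addition, state whether the further 25% cut in the 7.1b thrombocytopenia row is taken from the original or the current 5-FU dose.

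The clinical team should choose each rule; none is proposed here. The cost is a short amendment to Section 7, with no extra patients, visits or tests.
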